## **7.10 Special information excluded for verification of the hypothesis and the rationale (if applicable)**

Not applicable.

## 8. Monitoring Plan

Sponsor will appoint Monitors to regularly monitor the clinical trial institutions participating in the clinical trial to ensure that the clinical trial is conducted in accordance with the study protocol, ethics committee requirements and relevant regulations. The Monitors' monitoring plan is as follows:

- (1) Site initiation visit in each clinical trial institution: it will be held after the approval of the Ethics Committee and the signing of the clinical trial agreement. The purpose is to ensure that investigators and study teams obtain necessary training, fully understand the clinical trial plan and other study documents, and ensure that the documents and clinical supplies required for clinical trials are in place before the site initiation visit.
- (2) Monitoring visit of first patient enrolment in each clinical institution: The visit will be conducted as soon as possible after the first subject is enrolled in the clinical trial institution. The purpose is to ensure that the enrolled subjects met the inclusion criteria of the clinical trial, that all required examinations are completed, that the investigators and their study team fully understand the requirements of the clinical trial, and that issues are discovered and dealt with in advance.
- (3) Routine monitoring visit in each clinical institution: After the initiation to the end of the clinical trial, monitoring visits will be conducted every two weeks for the first two months of the enrollment period, and once a month thereafter, to ensure that all the enrolled subjects meet the inclusion criteria of the clinical trial, complete the required examinations, and receive smooth treatment of the enrolled subjects. Verify 100% of data in case report form and source data to ensure proper management of adverse events, follow up and resolve existing issues. Any change in the monitoring plan shall be approved by Sponsor in advance.
- (4) Site Close Visit: after all subjects have completed follow-up visits, clinical trial report and all existing problems have been properly resolved. The purpose of which is to ensure that investigators and clinical trial institutions fully understand the requirements of clinical trial archiving and the possible auditors of clinical trials by regulatory authorities.
- (5) Monitor will complete the monitoring report after each monitoring visit.

## 9. Data Management

### (1) Database setup

In this trial, an electronic data capture system is proposed to be used to establish the database, which conforms to the *Technical Guideline for Electronic Data Capture for Clinical Trials*. Each center has its own account and password, and the investigators of each center shall properly keep the account information.

### (2) Data entry

Before the official use of the database, the data management department shall draft the instructions for use of the database, and provide the investigators with training on the use of the database. The monitors shall complete the training for the investigators and keep the training records before the formal input of information.

### (3) Data verification

The project manager and statistician shall attend the meeting to discuss the draft version of data verification plan, and all contents of the meeting must be recorded.

The data verification plan shall focus on the following items: inclusion and exclusion criteria, logicality and consistency verification, missing items verification, time window verification, protocol deviation

verification, baseline data verification, medication as well as adverse events and serious adverse events during hospitalization and follow-up periods.

#### (4) Data query

The data query comes from medical and procedure verifications; all data queries must be verified against the corresponding case report form. Those that cannot be verified by a computer program shall be subject to manual verification, which must include all data points.

The monitor shall resolve each batch of electronic data queries according to the schedule and feed them back to the data management department.

#### (5) Database locking and transfer

The database shall be locked if the following conditions are met:

All queries are resolved and data updated; the statistical analysis plan is finalized.

The database locking document shall be signed after all the previous conditions are met. The clinical data specialist shall transfer the final database to the statistician for statistical analysis after the database is locked.

## 10. Feasibility Analysis

### 10.1 Feasibility analysis of success

JuggerStitch™ is made of all-soft material, which has little interference and trauma to surrounding tissues. Under unique in design, the two soft anchors are connected by a knot-free, self-locking suture ring. Compared to implants that use sliding knots to lock the repair site, the technique improves meniscal tissue retention and the surgeon's control over the repair site. The operation is simple with complete suture and no knot. Compared with the existing mainstream products, the mechanical properties are more than 60% higher, and the success rate of surgery can be greatly improved.

Meanwhile, JuggerStitch™ has been launched in the United States and has a certain clinical application basis in the United States. No serious safety events, such as serious adverse reactions and device deficiencies have been found since the device was launched. Due to the low risk of injury of the medical device used in this trial, subject compliance is high and the possibility of case drop is low.

All the clinical trial institutions participating in this clinical trial are authoritative entities in the field of orthopedics or sports medicine in China, and have medical equipment and resources that can meet the requirements of this clinical trial; all participants have high level of medical literacy and professional qualifications, which provides professional technical support for the design and implementation of this clinical trial protocol. At the same time, since the investigational medical device has been marketed abroad, and this clinical trial is to verify its safety and efficacy to provide support for marketing and registration in China, this clinical trial is expected to have quite high probability of success.

### 10.2 Feasibility analysis of failure

#### 10.2.1 Analysis of risk factors regarding the investigational medical device

This clinical trial is to implant the investigational medical device through the arthroscopic shoulder surgery, and the potential adverse events (AEs) possibly related to the surgery include infection, deep vein thrombosis, brachial plexus spasm, cardiogenic shock, severe respiratory depression, and articular cartilage injuries, etc. after implantation of the investigational medical device, adverse events may occur, including nonunion or delayed union of bone, damage to implant or implant rupture, implant migration or loosening, rejection of the body to the implant, pain or paresthesia due to the presence of the implant, osteonecrosis, poor healing, bone cyst formation, and secondary cartilage injuries. However, these risks have been specified in the ICF, and the subjects participating in this study will not have additional risks due to the

treatment or receive other additional auxiliary tests or treatments. Moreover, this investigational medical device is a marketed product approved by the US FDA and has been applied for clinical use in the US for over 2 years. No SAEs definitely or possibly related to the device have occurred during its use.

### **10.2.2 Analysis of the risk of investigator-related bias in the clinical trial**

The investigators participating in this clinical trial will be properly trained, and the clinical trial procedures and treatment as well as the collection of follow-up data will be implemented in compliance with the requirements of relevant standards. In addition, the clinical trial institutions conducting this clinical trial are all excellent teams in sports medicine in China, with excellent experience and techniques in clinical treatment and surgery. As such, the risk of failure caused by investigators is low.

### **10.2.3 Analysis of risks regarding the subjects**

Since the investigational medical device has high requirements for early postoperative rehabilitation exercise, the early engagement of the subjects in postoperative rehabilitation exercise may lead to failure of the investigational medical device and AEs. At the same time, the excessive withdrawal of subjects due to the failure of the investigational medical device and AEs may also lead to the failure of the clinical trial. The investigational medical device is designed to be an innovative soft anchor, with small damage caused at implantation. The control device (Fast-Fix 360) is also a product that has been marketed abroad for many years and has been applied for clinical use in China for a certain number of years. Considering this, the subjects are expected to have good compliance, and the medical staff participating in the study will provide appropriate education on the precautions for postoperative rehabilitation for the subjects. As a result, the subjects are less likely to withdraw from the trial due to the failure of the investigational medical device postoperatively.

## **11. Quality Control of the Clinical Trial**

### **(1) Qualification of clinical study personnel**

Investigators participating in the clinical trial must have the professional expertise, qualifications and abilities in conducting clinical studies, and pass the qualification review. The personnel requirements shall be relatively constant.

### **(2) Training of clinical study personnel**

The monitoring entity of this clinical study will be responsible for training the investigators and relevant staff from various clinical study institutions involved in this study before the initiation of this clinical study on the protocol and the conduct of this clinical study, to ensure that the personnel for the clinical study have adequate understanding and knowledge of the overall situation of the study, protocol, case report form, etc.

### **(3) Monitoring**

Authorized clinical monitors with professional experience in clinical studies will visit clinical study institutions on a regular basis according to the monitoring plan to verify their compliance with the protocol and regulatory requirements, and to conduct raw data verification.

### **(4) Inspection and audit**

The medical products regulatory authorities and the sponsor may entrust inspectors/auditors to conduct systematic inspection/audit on the activities and documents related to this clinical trial so as to evaluate whether the trial is conducted in accordance with the clinical trial protocol, SOP and relevant regulatory requirements, and whether the data of the trial is recorded authentically, accurately and completely in a timely manner.

## 12. Ethical Issues of the Clinical Trial and Informed Consent

### 12.1 Ethical considerations

Informed consent of the subjects is a protective measure for the subjects. Before the start of the clinical trial, investigators must have explained the details of this clinical trial to the subjects or their guardians to allow them fully understand and obtain the informed consent. The clinical trial cannot be started until the ICF is signed. If any important updated information related to the investigational medical device is found during the clinical trial, the ICF must be revised accordingly in writing and submitted to the ethics committee. After re-approval, the clinical trial may continue only after the reacquisition of the subjects' informed consent.

### 12.2 Approval of the clinical trial protocol

This clinical trial must follow the *Good Clinical Practice for Medical Devices*. Before the clinical trial, investigators must submit the clinical trial protocol, ICF and other relevant documents to the medical ethics committee of the hospital where the entity responsible for the clinical trial is located. The clinical trial can only be started after the approval of the ethics committee. Any change to the study protocol can only be implemented after the approval of the ethics committee.

### 12.3 Informed consent process and text of the ICF

#### 12.3.1 Informed consent process

During the screening of subjects, investigators must explain to the subjects or their guardians the details of this clinical trial, including the content, risks of the clinical trial and subjects' rights and interests, elaborate the contents of the ICF, and seek the patients' opinions on their willingness to participate in the clinical trial. The benefits and risks of this trial must be fully explained to ensure that the patients participating in the trial have undergone adequate informed consent process.

Incapacitated subjects may also enter the clinical trial if the ethics committee agrees in principle and the investigators believe that the subjects' participation in the clinical trial is in their own interests. However, the ICF shall be signed by their guardians and dated before the trial.

When neither the subjects nor their guardians are able to read, a witness shall be present during the informed consent process. After detailed explanation of the ICF, the witness will read the ICF and determine that its content is consistent with the orally informed content. Then the witness will sign and date the ICF with the verbal consent of the subjects or their guardians. However, it shall be noted that the signature of the witness and that of the investigator(s) shall be on the same day.

#### 12.3.2 Text of the ICF

The ICF will mainly include the following contents:

- (1) Introduction of the clinical trial project: project name, investigator, sponsor, version number or date of preparation; clarification of the purpose of the clinical trial; description of the process of the trial; statement of the time and duration of the subject's participation; the number and process of follow-up visits.
- (2) Description of the possible benefits, discomforts and risks of participation in this clinical trial.
- (3) Other alternative treatments for the conditions involved in the clinical trial.
- (4) Confidentiality of the clinical trial.
- (5) Clarification of the rights of subjects.
- (6) Explanation of the measures to deal with the injury caused to the subjects by the investigational medical device.

(7) Subject statement.

## 13. Provisions on Reporting of AEs and DDs

### 13.1 Adverse event (AE)

#### 13.1.1 Definition of AE

*Adverse Event (AE):*

An adverse event is any untoward medical occurrence, unintended disease or injury, or untoward clinical signs (including abnormal laboratory findings) in participants, users or other persons, whether or not related to the investigational medical device.

**Note 1:** This definition includes events related to the investigational medical device or the comparator.

**Note 2:** This definition includes events related to the procedures involved.

**Note 3:** For users or other persons, this definition is restricted to events related to investigational medical devices.

*Serious Adverse Event (SAE):*

A Serious Adverse Event is any adverse event that:

- a. led to death.
- b. led to serious deterioration in the health of the participant, that either resulted in:
  1. a life-threatening illness or injury, or
  2. a permanent impairment of a body structure or a body function, or
  3. in-patient or prolonged hospitalization, or
  4. medical or surgical intervention to prevent life-threatening illness or injury or permanent impairment to a body structure or a body function.
- c. led to fetal distress, fetal death or a congenital abnormality or birth defect.

**Note:** Planned hospitalization for a pre-existing condition, or a procedure required by the protocol, without serious deterioration in health, is not considered a serious adverse event.

*Adverse Device Effect (ADE):*

An Adverse Device Effect is an adverse event related to the use of an investigational medical device.

**Note 1:** This definition includes adverse events resulting from insufficient or inadequate instructions for use, deployment implantation, installation, or operation, or any malfunction of the medical device.

**Note 2:** This definition includes any event resulting from use error or from intentional misuse of the medical device.

*Serious Adverse Device Effect (SADE):*

A Serious Adverse Device Effect is an adverse device effect that has resulted in any of the consequences characteristic of a serious adverse event.

*Device Deficiency*

A Device Deficiency is defined as an inadequacy of a medical device with respect to its identity, quality, durability, reliability, safety or performance.

**Note:** Device Deficiencies include malfunctions, use errors, and inadequate labeling.

It is important to document in the study also all device deficiencies that could have led to a medical occurrence but did not lead to an adverse event.

The AEs that may occur during this clinical trial include:

### **1. AEs possibly related to the surgery**

Surgery-related events are divided into general surgical complications, anesthesia-related complications, articular cartilage injuries, postoperative haemarthrosis and peripheral nerve injury, etc.

- 1) General surgical complications include postoperative infection, deep vein thrombosis, etc.
- 2) Anesthesia-related complications mainly include brachial plexus spasm, cardiogenic shock, and severe respiratory depression, etc.
- 3) Headache caused by intraoperative controlled hypotension and neurological deficits caused by cerebral ischemia secondary to hypoperfusion.
- 4) Articular cartilage injuries are the most common complication of arthroscopic surgery. Cartilage injuries are difficult to repair, so the instrument used may not be forcefully inserted into the joint space or scratched on the surface of the cartilage during arthroscopy and arthroscopic surgery. Instead, the surgical operation shall be performed under direct visualization.
- 5) Postoperative haemarthrosis is a common postoperative complication, manifested as swelling and pain in the shoulder joint, and bloody fluid after arthrocentesis.
- 6) Postoperative paresthesia or paralysis of the nerves around the shoulder.
- 7) Intraoperative or postoperative fracture, and/or postoperative pain.

### **2. AEs possibly related to the investigational medical device**

- 1) Infection can lead to failure of the procedure.
- 2) Neurovascular injuries can occur due to surgical trauma.
- 3) Bending, fracture, loosening, rubbing, and migration of the implant may occur as a result of excessive activity, trauma, or load bearing.
- 4) Implantation of foreign materials can result in an inflammatory response or allergic reaction.
- 5) Inadequate healing, which may lead to breakage of the implant or failure of the graft material.
- 6) Pain, discomfort, or abnormal sensation due to the presence of the device.
- 7) Necrosis of bone or tissue.

### **3. Other AEs that occur during the trial.**

#### **13.1.2 Intensity of Symptoms**

For AEs, the severity or changes in severity shall be recorded at each follow-up visit. The following definitions of severity can be applied:

- **Mild:**  
The participant is aware of the sign or symptom, but finds it easily tolerated. The event is of little concern to the participant and/or little clinical significance. The event is not expected to have any effect on the participant's overall health or well-being.
- **Moderate:**

The participant has discomfort enough to cause interference with or a change in usual activities. The event is of some concern to the participant's health or well-being and may require medical intervention and/or close follow-up.

- **Severe:**

The event interferes considerable with the participant's usual activities. The event is of definite concern to the participant and/or poses substantial risk to the participant's health or well-being. The event is likely to require medical intervention and/or close follow-up and may be incapacitating or life threatening. Hospitalization and treatment may be required.

**Note:** The term “severe” refers to the intensity of the event and can be used with any event, without regard to whether or not it meets the criteria for being classified as “serious” or “unanticipated”. For example, a participant can have a severe headache, but it is not a serious event.

### **13.1.3 Outcomes between AEs and the surgery or investigational medical device**

#### Outcome Definitions

The outcome is in relationship to the Adverse Event, not the treatment rendered for the event (if any).

- **Resolved:** The adverse event has been resolved and/or no further treatment is required to treat the reported condition or illness.
- **Tolerated:** The adverse event will most likely never be resolved. The participant “tolerates” the illness or condition as a matter of life.
- **Pending:** Treatment or diagnostic studies were prescribed for the adverse event and the outcome of the adverse event is not yet known.
- **Study Withdrawal:** Due to the adverse event, the participant was withdrawn from the study.
- **Device Removal:** The adverse event resulted in the removal of a study device.
- **Reoperation of Affected Joint:** The adverse event resulted in reoperation of the study joint, but the reoperation did not include removal of a study device.
- **Death:** The outcome indicates the participant died as a direct result of the reported adverse event.

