### **13.1.4 Recording of AEs**

Investigators must record in detail all AEs (signs and symptoms) that have occurred in the study on the corresponding CRFs, including those reported by the patients voluntarily or observed during or after the treatment.

The records of the AEs shall describe the following:

- (1) Name.
- (2) Date of occurrence.
- (3) Date of resolution/relief (duration).
- (4) Determination of the severity of the AE.
- (5) Investigators must make judgment on the possible causality between the AEs and the investigational device or surgery.
- (6) Actions taken (if any).
- (7) Outcome.

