#### Reporting and Documentation of Adverse Events and Adverse Device Effects

Adverse Events and Adverse Device Effects (Table 1) have to be documented on the Adverse Event Report form over the whole time of the investigation including information on the date of onset, treatment and resolution, as well as assessment of both the seriousness and the relationship to the study device. Adverse Events that are deemed unrelated to the investigational device, the study protocol or procedure by the investigator will not be reported or followed. Further, the outcome of complications has to be documented and any changes in outcome are to be updated during the course of the study. In case of early termination of the study, further follow-up of the patient shall proceed according to the hospital's standard procedure.

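### The adverse event outcome code Resolved admits events that persist untreated, and its list mixes event status with reoperation, device removal and withdrawal

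*Combined protocol and SAP*

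**What the plan says.** Section 13.1.3 opens its outcome definitions with a principle: "The outcome is in relationship to the Adverse Event, not the treatment rendered for the event (if any"). It then gives seven codes: Resolved, Tolerated, Pending, Study Withdrawal, Device Removal, Reoperation of Affected Joint, and Death. The ones that matter here are:

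- Resolved is defined as follows: "The adverse event has been resolved and/or no further treatment is required to treat the reported condition or illness".
- For Tolerated, the condition set is: "The adverse event will most likely never be resolved". The person lives with it.
- Pending applies when treatment or a diagnostic work-up has been ordered and the result is awaited.
- Study Withdrawal applies when the event made someone leave the trial.
- Device Removal applies when the event caused an implant to be taken out.
- Reoperation of Affected Joint covers repeat surgery on the knee that leaves the implant in place.

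Section 13.1.4 lists seven things that an adverse event record must describe. Outcome is one item, the last. Actions taken is a separate item, and so is a date that covers either resolution or relief. Section 13.4 says that "the outcome of complications has to be documented and any changes in outcome are to be updated during the course of the study", and makes the same demand for serious events. It gives no rule for keeping an earlier code.

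**The concern.** An outcome code should tell the reader what state the event was in at last observation. A rule that lets Resolved mean that nothing more is being done cannot do this. A residual numb patch or a persistently painful knee that is simply left alone can carry the same code as a complication that cleared completely.

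The second difficulty is that the list describes more than one kind of thing. Device removal and reoperation are interventions, and withdrawal is a participant's disposition. An event can have any of these and also have a clinical status. If one value must serve for all, something is lost.

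The stake is how well the report describes persistent harm and repeat surgery. Safety is part of the stated objective, and this list is the only place where the protocol gives codes for reoperation and device removal. Section 6.1.3 describes no masking, so the person choosing between two permissible codes may know the arm.

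**Working it through.** No arithmetic applies. The check is whether the seven codes are mutually exclusive, whether they cover the possible states, and what the recording rules do to them.

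**Step 1: sort the codes.** Three give the current state of the event (Resolved, Tolerated, Pending) and one gives a fatal outcome (Death). The other three describe something else: two interventions and one disposition. That is 4 + 3 = 7. The two interventions conflict directly with the section's opening principle.

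**Step 2: try the wording on four plausible events.**

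| Event | Codes whose wording is met |
|---|---|
| Sensory deficit judged permanent, no treatment needed | Resolved (second half) and Tolerated |
| Sensory deficit still present, may improve, nothing prescribed | Resolved (second half) only |
| Retear reoperated without device removal, knee then settles | Reoperation of Affected Joint, then also Resolved |
| Pain that leads to withdrawal, treatment under way with result unknown | Study Withdrawal and Pending |

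The first row shows overlap with no precedence rule: two sites could code the same deficit differently and both comply. The second shows a gap. Tolerated needs near-certain permanence and Pending needs something to have been prescribed, so an event in between has no status code except Resolved. The protocol foresees events of this kind: section 13.1.1 lists abnormal sensation and pain among the possible device-related events, and altered sensation among the surgical ones.

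**Step 3: apply the update rule.** In the third row, the outcome changes when the knee settles, and section 13.4 requires that change to be entered. If the form holds one outcome value, Reoperation of Affected Joint is replaced by Resolved. If it holds several values or keeps a history, nothing is lost. Likewise, in the fourth row a single-value form left at Study Withdrawal shows no clinical status, and one later updated no longer shows the withdrawal.

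**Step 4: find where the code is used.** The safety analysis in section 7.1.2 counts events such as pain, loosening and retear at stated times, and describes type, frequency and relation to the device. None of this uses the outcome code. That section also says that cases suspended because of adverse events will be noted specifically; a listing of those could draw on the withdrawal code.

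**The case against.** The strongest reply is that the outcome code carries little weight. No planned table uses it. A retear counts as a retear whatever its outcome, and the device-related adverse event rate depends on attribution. This stands and limits the consequence.

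Second, the information is held elsewhere. Treatment is recorded under section 13.1.4 (actions taken) and again under section 13.4. Permanent impairment is among the seriousness criteria in section 13.1.1. Section 13.1.2 asks for severity, or changes in it, at each follow-up visit, and section 7.7 requires reasons for withdrawal to be explained in the report. This largely stands too: a reoperation need not vanish from the record. It would, however, sit in an item for which the protocol gives no codes.

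Third, Tolerated already provides for a permanent injury. True, but that leaves the overlap without a precedence rule and does nothing for the event that may still improve.

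Fourth, a single overwritten field is an inference. Neither the case report form nor the adverse event form is in the documents. That is correct, so the loss of a code on update can be stated only conditionally.

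A reader might go further and infer that the planned safety tables understate persistent harm or reoperation by arm. The documents do not support that, because no table by outcome code is planned. A reader might also try to size the problem from the 22.4% Fast-Fix failure rate in section 4.2, where failure means need for reoperation. That figure comes from a review of bucket-handle tears, while eligibility here is wider, and it describes how often repairs fail, not how often an outcome is miscoded.

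**Conclusion.** The point holds, as a minor one. Two parts rest on the text alone: Resolved does not require resolution, and the list contradicts its opening principle by placing interventions and a disposition among event states. A third part, the replacement of a reoperation, removal or withdrawal code by Resolved, assumes that the form stores one current outcome value.

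The reach is confined to listings or tables of adverse event outcome, reoperation, device removal and withdrawal in the clinical study report. The primary endpoint, the device-related adverse event rate and the section 7.1.2 counts by type do not change. The number of events affected cannot be estimated from the documents. Nothing shows that coding would differ between arms; the wording only leaves room for it.

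**What to change.** In section 13.1.3:

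1. Delete the second half of the Resolved definition, so that the code requires the event to have gone.
2. Make event status a single choice among exclusive codes, adding ongoing and resolved with sequelae. Either fold Tolerated and Pending into ongoing or state the boundary between them, so that the new codes do not create a fresh overlap.
3. Take Device Removal, Reoperation of Affected Joint and Study Withdrawal out of the status list. Record each as a separate yes/no item with a date that later status updates cannot overwrite, and list them by arm in the report.

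The cost is a protocol wording change, a revised adverse event form with a few added fields, and recoding of events already entered. Fewer events will be counted as resolved. No new visits or assessments are needed. The change is best made before database lock, because an overwritten code may be recoverable only from source records. If the form cannot be changed, deleting the second half and stating a precedence rule would remove the overlap, but would not supply an ongoing code or protect the three other items.
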